Aim #4: To compare the overall cost. There are several differences between the two surgical reconstruction methods as outlined in the background. The differences have implications for reducing several factors associated with operative time. The average decrease in operation time for orbital reconstruction with selective laser-melting patient-specific implants is 0.40–3.82 hours.⁽¹⁷⁾

- **Hypothesis #4:** The total overall operative cost will be significantly **lower** than for non-patient-specific orbital implants.

BACKGROUND

Facial trauma is among the most common traumas seen in urban trauma centers,⁽¹⁾ and orbital fractures are common in blunt facial trauma. The 3 patterns of orbital fractures are linear, complex, and isolated orbital floor fractures. Linear orbital fractures do not result in a defect. Complex orbital fractures involve extensive facial fractures that affect 2 or more orbital walls and are usually associated with Le Fort II and Le Fort III fractures. Isolated orbital floor fractures affect only one wall, with less than a 2-cm-diameter defect.⁽¹⁸⁾ The incidence of orbital fractures among all facial fractures is approximately 49%; this rate changes depending on the study. Complex orbital fractures represent 66% of all orbital fractures,⁽¹⁹⁾ and 22%–47% are isolated orbital floor fractures.^(3, 12)

Over the past two years, GMH has cared for 90 isolated orbital floor fractures. With respect to the **total orbital fractures (complex and isolated types), these numbers increased to 126 cases over the years 2016 and 2017.** Indications for surgery include retrobulbar hematoma, inferior rectus muscle entrapment, enophthalmos larger than 2 mm during the first 6 weeks, fracture involving more than 50% of the orbital floor, and diplopia in the primary field of gaze that fails to resolve after 2 weeks.^(3, 7) Titanium mesh is the current recommended material due to its availability, biocompatibility, cost-effectiveness, and low susceptibility to infection.^(12, 20)

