The primary outcome variable is the orbital volume of the injured orbit compared to the contralateral uninjured orbit as assessed by CT scan with OsiriX medical imaging software (OsiriX MD 8.5.2) **at immediate post-operative hour**.

Accordingly, the primary outcome variable will be classified as:

- A. The absolute reduction in orbital volume from the measured post-traumatic volume, as measured by CT.

The secondary outcome variables will be recorded 1 week, 3 weeks, and 6 weeks postoperatively.

The secondary outcome variables include the following:

- 1- Adequate orbital volume reduction, defined as a reduction of orbital volume to **less than 2 cm³**.
- 2- Unsatisfactory orbital volume, defined as a final orbital volume **more than 2 cm³**
- 3- Post-operative variables: enophthalmos, infection, infraorbital nerve injury, traumatic pupillary mydriasis, orbital compartment syndrome, extra-ocular motility, and plate contour.
- 4- Operating time.
- 5- Length of stay (LOS).
- 6- Treatment charges.

The following are details regarding secondary outcome variables:

- Enophthalmos as assessed by clinical examination using a Hertel exophthalmometer.
 - A difference of more than 2 mm between the two orbits is diagnostic for enophthalmos.⁽⁴⁾
- Infection
 - As defined by the presence of post-operative pus in the wound, a sinus tract or fistula, or elevated WBC >11.0x10⁹/L combined with erythematous skin and swelling on the operated side more than on the un-operated side.
- Infraorbital nerve injury as assessed by clinical examination using neurosensory testing (NST).
 - i. NST is a standardized methodology designed to objectively evaluate sensory nerve function.⁽²²⁾ The sensory impairment is determined by 3 levels of testing; each level classifies a specific type of sensory nerve injury.^(22, 23)
 - ii. All patients will be assessed for the development of altered sensation of the infra-orbital nerve that:
 - A. Did not present prior to the surgery.
 - B. Did not improve after the surgery.
- Traumatic pupillary mydriases as assessed by pupillary size measurement in millimeters.
 - All patients will be assessed for the development of post-operative traumatic pupillary mydriasis that did not present prior to the surgery.
- Orbital compartment syndrome as assessed through clinical examination using tonometers.
 - Intra-ocular pressure (IOP) > 40 mmHg is diagnostic of orbital compartment syndrome.

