We expect a **sample size of 60** surgical cases, evenly split between the new treatment and control groups, to have a study powered to **detect at least a 1 cm³ difference in orbital volume** between the groups. The sample size calculation was based on using a two-sample Student's t-test to compare the difference in contralateral orbital volume between the treatment and control groups. We used a **power of 90%**, alpha level of .05, and 1.17 cm³ standard deviation of orbital volume. The 'normal' orbital volume and standard deviation were estimated from the results of Forbes et al. (1984). Sample size calculations were performed with the 'power.t.test' function in R statistical software based on Cohen (1988).⁽²⁵⁾ Taking attrition into account, if 25% of our expected patient enrollment numbers are not met for any reason, **our study would still retain a power of 80%**. Additionally, in the event of attrition from loss-to-follow-up alone, our primary outcomes variable and the bulk of the secondary outcomes variables, including the reduction of orbital volume to less than 2 cm³, operative time, traumatic pupillary mydriasis, orbital compartment syndrome, extra-ocular motility, and plate contour, will be successfully obtained on immediate post-operative hour. **Attrition at these stages will have no effect on the above variables.**

Randomization & Statistical Analysis

Cases will be randomized to the treatment or control arms using a pre-generated block randomization scheme with a **block size of 4** and stratified according to surgeon/specialty. In essence, each surgeon will receive their own list of randomized cases to simplify the logistics of the trial. **The block randomization guarantees that at no point during the trial will there be more than a 3-case difference between the treatment and control arms for each individual surgeon**; thus, it is possible but unlikely that there will be a maximum 9 case difference at some

point (sizes will be equal at completion). The randomization scheme has been pre-generated by a statistician, and the resulting trial arm for each case will be placed in envelopes to be revealed at the time of patient enrollment. The treatment will not be blinded to the physician or the patient; it is not practical to keep knowledge of the procedure concealed.

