- Complex orbital fractures will be exposed and identified via a transconjunctival approach in combination with lateral cantholysis if needed to improve access.
- To record and compare the operative time between the two groups, a stopwatch will be utilized. The time in minutes will be recorded from fracture exposure and identification to final implant placement and fixation.

Postoperative Assessment

During post-operative care, all patients will undergo the following:

- 1) Maxillofacial non-contrast CT scans according to the protocol will be obtained as part of the standard of care in managing orbital fractures.
- 2) The PI will evaluate the orbital volume using OsiriX (medical software). Orbital volume measurements will be obtained to compare the injured and uninjured (contralateral) orbital volumes. OsiriX MD offers advanced processing techniques and has the ability to precisely measure orbital volume. It utilizes the DICOM data from the immediate post-operative CT scans.
- 3) All patients, regardless of the group into which they are randomized, will receive their post-operative assessment by the designated team resident under the supervision of one of the following attendings: [name] for OMFS, [name] for ENT, or [name] for Plastic Surgery.
- 4) All patients, regardless of the group into which they are randomized, will receive their post-operative ocular assessment by [name], ophthalmology attending and Co-PI, or by her fellow [name].

Follow-Up

- All patients will be regularly assessed at 1 week, 3 weeks, and 6 weeks postoperatively.

This is a standard post-operative follow-up schedule for craniomaxillofacial fracture patients. It is also an adequate duration for edema to resolve, which will assist in the accurate evaluation of enophthalmos. The following will be evaluated and recorded by the surgical team at each follow-up visit: enophthalmos, infection, infraorbital nerve injury, traumatic pupillary mydriasis, orbital compartment syndrome, and restricted extra-ocular movement.

- In terms of data collection and data extraction from Epic: PI [name], co-PI [name] and an assigned research coordinator will be involved.

Patient Compensation

All patients enrolled in the study will be compensated with \$100 for their time and to encourage compliance. Their compensation includes the costs of participation in the study (\$50) and the completion of the follow-up visits at week 6.

Data Collection & Analysis

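### As literally written, the 2 cm³ rule for adequate or unsatisfactory orbital volume is applied to the orbit's own volume, not to its difference from the uninjured side

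*Combined protocol and SAP*

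**What the plan says.** In the Methodology (Study Settings and Patients), secondary outcome 1 reads "Adequate orbital volume reduction, defined as a reduction of orbital volume to" less than 2 cm³. Secondary outcome 2 reads "Unsatisfactory orbital volume, defined as a final orbital volume" "more than 2 cm³". Neither item mentions the other orbit. The sample-size section repeats the first item among the variables available immediately after surgery: "including the reduction of orbital volume to less than 2 cm³".

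Other parts of the plan do compare the two orbits:

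- The primary outcome: "The primary outcome variable is the orbital volume of the injured orbit compared to the contralateral uninjured orbit".
- The sample-size section bases its t-test on the contralateral difference.
- Postoperative Assessment: "Orbital volume measurements will be obtained to compare the injured and uninjured (contralateral) orbital volumes".
- Enophthalmos, under the same list of secondary outcomes, is defined as a gap of more than 2 mm between the orbits.

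On timing, the lead-in to the secondary outcomes says they are recorded at 1, 3 and 6 weeks. The sample-size section places this one at the immediate post-operative hour.

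**The concern.** The quantity named in item 2 is the final volume of the orbit. If whole orbits are much larger than 2 cm³, nobody can meet the adequate definition and everybody meets the unsatisfactory one, whichever implant was used. These two items carry the plan's only adequate/unsatisfactory threshold for volume, so they would supply the clinical reading of the volume result.

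The more realistic risk is that someone notices the problem at analysis and repairs the rule then. More than one repair is open and they do not agree. The PI reads the volumes, the treating physicians are not blinded, and no blinding is stated for the volume reading. A definition settled at that stage can be influenced by the results.

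**Working it through.** **1. The plan's own figure.** Inputs from Randomization Sample Size & Calculation: difference 1 cm³, SD 1.17 cm³, alpha .05, power 90%, two-sample t-test, equal arms. Sidedness is not stated; two-sided is assumed. The noncentral t calculation gives 30 per arm with power 90.2%, so 60 in total reproduces. At 22 to 23 per arm (25% shortfall, 45 in total) power is 79.1% to 80.9%, which matches the stated 80%. The 2 cm³ rule enters none of this.

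**2. The rule taken literally.** The documents give no normal orbital volume, so the mean volume *m* is an assumption. With a normal model and SD 1.17 cm³:

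P(volume < 2) = Φ((2 − m)/1.17), and P(at least one of 60 adequate) = 1 − (1 − P)^60.

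| Assumed mean *m* (cm³) | z | P per patient | P(any of 60) |
|---|---|---|---|
| 5 | −2.56 | 0.0052 | 27% |
| 5.67 | −3.14 | 0.00085 | 5.0% |
| 6 | −3.42 | 0.00031 | 1.9% |
| 7 | −4.27 | 0.0000096 | 0.06% |
| 10 | −6.84 | 4 × 10⁻¹² | about 2 × 10⁻¹⁰ |
| 20 | −15.4 | 1 × 10⁻⁵³ | effectively 0 |
| 30 | −23.9 | 7 × 10⁻¹²⁷ | effectively 0 |

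Above about 6 cm³ the expected result is 0/30 versus 0/30 adequate, for which Fisher's exact test gives p = 1.0.

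**3. The possible repairs disagree.** Let D be injured minus uninjured volume after surgery, and R the reduction from the post-traumatic volume. R is a candidate because the primary outcome is itself classified as an absolute reduction from that volume. Three hypothetical patients:

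| Patient | Absolute: \|D\| < 2 | Signed: D < 2 | Amount: R < 2 |
|---|---|---|---|
| Starts 4 above the healthy side, ends level (D = 0, R = 4) | adequate | adequate | not adequate |
| Starts 4 above, ends 3 above (D = 3, R = 1) | unsatisfactory | unsatisfactory | adequate |
| Starts 4 above, ends 3 below (D = −3, R = 7) | unsatisfactory | adequate | not adequate |

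The amount reading reverses the meaning for the first two patients. The signed and absolute readings part company on over-correction. Assuming an SD of D of 1.17, the share of patients more than 2 cm³ too small is Φ(−2/1.17) = 4% if an arm averages D = 0, and Φ((−2 + 1)/1.17) = 20% if it averages D = −1.

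**4. After the repair to |D| < 2.** P(adequate) = Φ((2 − μ)/1.17) − Φ((−2 − μ)/1.17). Assumptions: SD of D 1.17, arms 1 cm³ apart, control mean μ from 1 to 3 cm³. Power is approximate: normal approximation for two proportions, pooled variance under the null, two-sided .05, 30 per arm.

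| Control μ | Adequate, treatment | Adequate, control | Power |
|---|---|---|---|
| 1 | 91% | 80% | 24% |
| 1.5 | 88% | 66% | 53% |
| 2 | 80% | 50% | 69% |
| 2.5 | 66% | 33% | 73% |
| 3 | 50% | 20% | 70% |

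The outcome then carries information, though with less power than the continuous primary comparison.

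**The case against.** The strongest reply is that nobody would apply the rule literally. The primary outcome, the sample-size basis and the post-operative measurement all compare the injured with the uninjured orbit, so a competent analyst would take a difference. That is a fair account of the probable intent, and a report of 0 of 60 adequate is unlikely. It does not settle which difference is meant, and the wording appears in two sections, so it is not an isolated slip.

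Three stronger readings are tempting, and the documents do not support them.

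- *That the documents themselves show every orbit to exceed 2 cm³.* They give no orbital volume. The Background sentence "Isolated orbital floor fractures affect only one wall, with less than a 2-cm-diameter defect" might seem to offer a scale, since a sphere 2 cm across holds 4.19 cm³. But it describes a hole in one wall, not the orbit, and it is an upper limit. A sphere 1.5 cm across holds 4/3 × π × 0.75³ = 1.77 cm³, below the cut. The literal consequence therefore rests on an assumed mean volume.
- *That Aim 1 is left without information.* The continuous primary outcome tests Aim 1 and does not use the threshold.
- *That the separate listing of two complementary categories, or the unassigned value of exactly 2 cm³, does harm of its own.* The first is redundancy, and the second hardly matters for a continuous CT measurement.

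It is also fair to say that an absolute difference decides something the plan leaves open. The plan speaks of volume reduction and links failure to restore volume to enophthalmos, so a one-sided residual excess is a possible intent. The sponsor should confirm the direction.

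**Conclusion.** The concern holds as a defect in the definition of secondary outcomes 1 and 2. As literally written, they apply the 2 cm³ cut to the orbit's final volume. Under a normal model with SD 1.17 cm³ and any mean volume above about 6 cm³, essentially every patient in both arms would be unsatisfactory and the outcome could not distinguish the implants. The mean volume is an assumption, but the conclusion is insensitive to it: it is the same throughout the 10 to 30 cm³ range examined. The practical exposure is an unspecified choice among readings that classify patients differently, made after the data are available. The primary outcome, its analysis and N = 60 stand. This should be corrected, but it does not threaten the main result.

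**What to change.** Replace items 1 and 2 with one binary secondary outcome: adequate if the absolute difference between injured and uninjured orbital volume on the immediate post-operative CT is less than 2 cm³, and unsatisfactory otherwise (2 cm³ or more). The threshold remains the sponsor's.

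With it:

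- State that over-correction by 2 cm³ or more counts as unsatisfactory. This fits Hypothesis 1, which concerns accurate restoration of pre-trauma volume. Have the sponsor confirm that this is the intended direction.
- Bring the wording in Randomization Sample Size & Calculation into line.
- Correct the lead-in to the secondary outcomes so that this item is tied to the immediate CT and not to weeks 1, 3 and 6.

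The cost is a few lines of protocol text, ideally settled before any volumes are compared by arm. Both orbits are already measured on that scan, so no extra imaging, visits or patients are needed.

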Traditional methods of orbital fractures reconstruction involve intra-operative shaping of orbital implants (titanium mesh). ⁽¹⁰⁾ Orbital fracture reconstruction using selective laser-melting patient-specific implants has been found to be superior to traditional reconstruction methods. ^(8, 11, 12) The challenges with the traditional approach are a significant increase in cost and longer preoperative time (production time). ^(11, 12) There have been no comparisons published between the traditional approach and pre-adjusted patient-specific orbital implants with respect to orbital volume reconstruction.

- Hypothesis #1: Pre-adjusted patient-specific orbital implants will **more accurately restore the orbital volume** to pre-trauma measures than non-patient-specific orbital implants.

Aim #2: To compare postoperative complications.

The main complications due to orbital fractures reconstruction are 1) enophthalmos and 2) diplopia as a result of inadequate orbital volume reconstruction. The incidence of enophthalmos after the traditional orbital reconstruction approach is 7–27%. ^(5, 13, 14) This rate is significantly higher than that observed after using the patient-specific approach (3.7%). ⁽¹²⁾ Again, there are currently no data regarding pre-adjusted, patient-specific orbital floor implants. The incidence of

diplopia after the traditional orbital reconstruction approach is 8–42%,^(14–16) which is significantly higher than that for the patient-specific approach (3.2%).⁽¹²⁾

- **Hypothesis #2:** Pre-adjusted patient-specific orbital implants will **have fewer postoperative complications** than non-patient-specific orbital implants.

Aim #3: To evaluate the length of hospital stay. The typical hospital stay for an orbital floor fracture at Grady Memorial Hospital (GMH) is 1–2 days, depending on the patient's response to surgery.

- **Hypothesis #3:** Pre-adjusted patient-specific orbital implants lead to a **shorter length of stay**, secondary to improved accuracy of implant design, placement, and reduced need for manipulation. This would be expected to lead to decreased postoperative swelling and pain. Orbital fracture reconstruction could be executed as a same-day surgery (outpatient surgery) when utilizing 3DP.

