With such a 3D printer, true-to-life anatomic models can be made on-site within hours, and a patient with an orbital fracture can undergo reconstruction with a customized and personalized implant. An important difference compared with the virtual surgical planning (VSP) stereolithographic model is that the titanium implant is not milled on the model in 3DP. We use the over-the-counter titanium plates that are manually adjusted according to the printed model. We then send the plates to sterilization for preparation. Notably, this technology and method are yet to be applied to traumatic orbital floor fractures. Thus, to the best of our knowledge, this study is the first of its kind.

The purpose of this study is to compare (pre-bend) patient-specific orbital implants utilizing an office-based 3-D printer with standard non-adapted orbital implants (traditional approach). We will 1) preoperatively generate a patient-specific model to pre-adapt the titanium mesh to be used in unilateral orbital fractures; 2) accurately restore the orbital volume to the pre-injured measures; 3) prevent post-operative complications in terms of enophthalmos and diplopia; and 4) decrease the operative time, therefore decreasing the overall cost and increasing the value. Our patients greatly benefit from a fast and cost-effective method of reconstructing orbital floors due to the high volume and urban patient population of GMH.

METHODOLOGY

Study Settings and Patients

This is a prospective randomized clinical study with longitudinal follow-up. The study duration is 2 years. It will be conducted at GMH within the Grady Health System. The study targets urban adults suffering blunt facial trauma who are diagnosed with unilateral orbital fracture. Patients will be randomized into one of the following groups:

- Group A: patients who have orbital reconstruction utilizing **pre-adjusted patient-specific orbital implants with OB3DP (Treatment Group)**.

- Group B: patients who have orbital reconstruction utilizing **non-patient-specific** orbital implants (traditional approach) (**Control Group**).

The primary predictor variable is the treatment group (pre-adjusted patient-specific orbital implants utilizing OB3DP vs. non-patient-specific orbital implants).

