- Extra-ocular motility as assessed through clinical examination. The patient should be able to move the eyes through the six cardinal positions of gaze (left, right, up and right, up and left, down and right, down and left). All patients will be examined for the following:
 1. Development of restricted extraocular motility that was not present prior to the surgery.

2. Persistent restriction of extraocular motility after the surgery.

- Plate contour
 - Inability to achieve the normal orbital contour as assessed in the immediate post-operative CT scan.
- Operating time
 - This will be calculated from fracture exposure and identification to the final implant placement and fixation and will be recorded in minutes.
- Length of stay
 - 1- Isolated orbital floor fracture patients do not require a pre-operative hospital stay. Length of stay will be calculated in terms of post-operative hospital stay (days).
 - 2- Length of stay in cases of complex orbital fracture will be calculated in terms of pre-operative and post-operative hospital stay (days).
- Treatment charges

This will be calculated with consideration of the following:

- 1- Facility operating room charges, which include anesthesia time (surgical time multiplied by the facility rate of \$33/ minute).
- 2- Hardware charges (plates and screws).
- 3- LOS charges (LOS multiplied by the facility daily rate of \$1,690/ day).
- 4- The cost of the 3D printed model including the cost of the 3D printer and filaments (\$1.5).

All treatment charges variables will be provided by the GMH Financial Planning and Analysis center. Total treatment charges facility operating room charges, hardware charges, LOS, and the 3D printed model cost will be compared between groups in a manner similar to that outlined by Bouloux et al. ⁽²⁴⁾

Randomization Sample Size & Calculation

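### Diplopia is named in Aim 2 as one of two main complications, but post-operative diplopia is not pre-specified as an outcome, follow-up item or data-table row

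*Combined protocol and SAP*

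**What the plan says.** Under Specific Aims and Hypothesis, Aim #2 of the combined protocol and SAP opens: "The main complications due to orbital fractures reconstruction are 1) enophthalmos and 2) diplopia as a result of inadequate orbital volume reconstruction". It cites a diplopia incidence of 8–42% with the traditional approach and 3.2% with the patient-specific approach, and adds that "there are currently no data regarding pre-adjusted, patient-specific orbital floor implants". Hypothesis #2 is that pre-adjusted implants will "have fewer postoperative complications". The purpose paragraph at the end of the Background repeats the pair: the study will "prevent post-operative complications in terms of enophthalmos and diplopia".

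In the Methodology, item 3 of the secondary outcomes reads "Post-operative variables: enophthalmos, infection, infraorbital nerve injury, traumatic pupillary mydriasis, orbital compartment syndrome, extra-ocular motility, and plate contour". The definitions that follow cover each of these. Extra-ocular motility is scored as newly developed restriction or as "Persistent restriction of extraocular motility after the surgery".

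Preoperative Assessment includes binocular diplopia in the eye examination, as a component separate from extraocular motility. Postoperative Assessment, item 4, gives every patient an ocular assessment by ophthalmology but lists neither its components nor its timing. Follow-Up names six items that the surgical team records at weeks 1, 3 and 6. Diplopia is not one of them, and the Data Collection & Analysis table has no row for it at any time point.

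**The concern.** The aim and the measurement plan do not match. Aim #2 singles out two complications. Enophthalmos is carried through every later layer of the plan, with a definition, a method, visits and a data field. Diplopia drops out after the aims and purpose, and reappears only as an indication for surgery and as part of the pre-operative examination.

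Unresolved diplopia is among the indications in the inclusion criteria, so some patients will have it at entry. Their baseline is examined, but no matching item is planned after surgery. Whether diplopia resolved, persisted or was new would have to be pieced together from chart notes with no common definition or time point. A diplopia result assembled that way would not be pre-specified, and it would be open to criticism as selective reporting.

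**Working it through.** **1. Text check.** Each layer of the plan, for the two complications that Aim #2 names:

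| Place in the document | Enophthalmos | Diplopia |
|---|---|---|
| Aim #2 | named | named |
| Purpose, end of Background | named | named |
| Secondary outcomes, item 3 | listed | absent |
| Outcome definitions | Hertel, difference over 2 mm | absent |
| Preoperative Assessment | Hertel measurement | binocular diplopia examined |
| Follow-Up items | listed | absent |
| Data table, post-operative rows | weeks 1, 3 and 6 | absent |

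The table's general row for eye examination results is marked pre-operative only. The nearest post-operative row is extra-ocular motility with the gaze noted. The motility definition concerns restriction of movement and does not mention double vision. Because the pre-operative examination lists the two as separate components, motility cannot be read as the protocol's own stand-in for diplopia.

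**2. The plan's own figure.** The sample size concerns orbital volume: difference 1 cm³, SD 1.17 cm³, alpha .05 (two-sided assumed), power 90%. The standardised effect is 1/1.17 = 0.855. The exact two-sample t calculation gives 29.76, hence 30 per arm and 60 in total, with 90.2% power at 30 per arm. This reproduces the stated 60. The document gives no corresponding figure for diplopia.

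**3. What 60 patients could show on diplopia (illustration only).** Inputs: 30 evaluable per arm; control rates of 8% and 42% (the ends of the Aim #2 range) and 25%, an assumed midpoint, (8 + 42)/2; treated rate 3.2%, which Aim #2 cites for manufactured patient-specific implants, a different type from the pre-bent plate; two-sided alpha .05. Power is the sum, over all pairs (x, y) whose test gives p ≤ .05, of Bin(x; 30, p_control) × Bin(y; 30, 0.032). The analysis section allows chi-square or Fisher depending on prevalence, so both are shown.

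| Control rate | Expected cases, control (30 × rate) | Expected cases, treated (30 × 0.032) | Fisher power | Uncorrected chi-square power |
|---|---|---|---|---|
| 8% | 2.4 | 0.96 | 1% | 9% |
| 25% | 7.5 | 0.96 | 55% | 76% |
| 42% | 12.6 | 0.96 | 96% | 98% |

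By Fisher, 80% power is first reached at a control rate of about 32.2%. That threshold belongs to the test: at the same rate, uncorrected chi-square power is 91%. The treated rate matters as much. With 10% treated against 25% control, Fisher power falls to 21%. Fewer than 30 evaluable per arm at week 6 would also change these figures.

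**The case against.** The strongest reply is that diplopia may be captured anyway. Ophthalmology sees every patient after surgery, binocular diplopia belongs to what the protocol calls the standard examination for these fractures, and data extraction from the electronic record is planned. The outcome list is introduced as inclusive, and the analysis section provides tests for complications in general. Part of this stands. A reader might infer that the trial will be unable to say anything about diplopia, and the documents do not support that, because a charted finding may be retrievable. But no passage fixes a definition, a time point or a data field, and the sentence on abstracting examination data sits in the pre-operative section. Possible charting is not a planned outcome.

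A second reply is that motility by gaze, recorded at each visit, reflects one mechanism behind diplopia. That is true and gives partial coverage, but the protocol does not present it as a proxy.

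A third is that the comparison may have little power. Low power did not keep enophthalmos off the list: at its cited rates (7–27% against 3.7%), Fisher power at 30 per arm is about 1% to 60%. The reason to add diplopia is that Aim #2 names it, whatever the power.

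**Conclusion.** The point holds as a mismatch between aim and outcome: diplopia is named in Aim #2 and the purpose but is not pre-specified for measurement after surgery. Its reach is limited. It would be tempting to conclude that Hypothesis #2 as a whole is untestable. The documents do not support that, since the hypothesis is worded for complications in general and enophthalmos and the other listed items are planned. The primary outcome and N = 60 are untouched. This should be corrected, but it does not threaten the trial's main result.

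The conclusion rests on the text and not on the power figures, which depend on the test, on 30 evaluable patients per arm, and on a treated rate borrowed from another implant type.

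**What to change.** Add post-operative binocular diplopia as a secondary outcome in the outcome list and definitions, the Follow-Up items and the data table. Record it as present or absent, in which gaze, and as new or persistent against the pre-operative finding, using the pre-operative method. The surgical team already recording the other items can do this at the existing week 1, 3 and 6 visits. Where the ophthalmology assessment already takes place at a given visit, its record may be used. No extra ophthalmology visits are needed; the protocol gives that assessment no schedule, so its presence at those visits should not be assumed. Compare the arms at week 6, the last planned visit, with the planned chi-square or Fisher test, and state that the outcome is not powered.

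The cost is a few form fields and one more unpowered secondary comparison. Diplopia is also patient-reported, and neither patients nor physicians are blinded to treatment, so some reporting bias must be accepted and acknowledged.

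If the investigators do not intend to measure diplopia, the alternative is to remove it from Aim #2 and the statement of purpose, so that the trial makes no claim about it.
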